## Misuse

This refers to situations where the medicinal product is intentionally and inappropriately used in a manner not in accordance with the authorised product information.

## Non-serious

An AE or AR that does not fulfil the requirement for being an SAE or SAR.

## Occupational Exposure

An exposure to a medicinal product, as a result of one's professional or non-professional occupation. It does not include the exposure to one of the ingredients during the manufacturing process before the release of a finished product.

## Off-label use

Situations where a medicinal product is intentionally used for a medical purpose not in accordance with the terms of the marketing authorisation. Example include the intentional use of a product in situations other than the ones described in the authorised product information, such as a different indication in terms of medical condition, a different group of patients (for example, a different age group), a different route or method of administration or a different posology. The reference terms for off-label use are the terms of marketing authorisation in the country where the product is used.

## Outcome categories and definitions

- Recovered/resolved – The patient has fully recovered from the condition, or by medical or surgical treatment the condition has returned to the level observed at the first study related activity after the patient has signed the informed consent.

Protocol  
 Study ID: NN8640-4515  
 UTN: U1111-1264-8642  
 EU PAS No: Pending

**CONFIDENTIAL**

Date: 15 February 2022  
 Version: 3.0  
 Status: Final  
 Page: 43 of 53

**Novo Nordisk**

- Recovering/resolving – The condition is improving, and the patient is expected to recover from the event. This term is only applicable if the patient has completed the study or has died from another AE.
- Recovered/resolved with sequelae – The patient has recovered from the condition, but with a lasting effect due to a disease, injury, treatment or procedure. If a sequela meets a SAE criterion, the AE must be reported as a SAE.
- Not recovered/not resolved – The condition of the patient has not improved, and the symptoms are unchanged, or the outcome is not known.
- Fatal – (only applicable if the patient died from a condition related to the reported AE. Outcomes of other reported AE in a patient before he/she died should be assessed as “recovered/resolved”, “recovering/resolving”, “recovered/resolved with sequelae”, or “not recovered/not resolved”. An AE with fatal outcome must be reported as an SAE.
- Unknown – This term should only be used in cases where the patient is lost to follow-up.

## Overdose

This refers to the administration of a quantity of a medicinal product given per administration or cumulatively, which is above the maximum recommended dose according to the authorised product information. Clinical judgement should always be applied.

## Serious Adverse Event (SAE)

An SAE is an experience that at any dose results in any of the following:

- Death
- Life-threatening experience (actual risk not hypothetically)
- Inpatient hospitalisation or prolongation of existing hospitalisation
- A persistent or significant disability/incapacity or is a congenital anomaly/birth defect
- Important medical events that may not result in death, be life-threatening or require hospitalisation may be considered an SAE, when based upon appropriate medical judgement - they may jeopardise the patient or subject or require medical or surgical intervention to prevent one of the outcomes listed in this definition. Suspicion of transmission of infectious agents must always be considered an SAE.

**Note:** Hospitalisation for elective treatment of a pre-existing condition that did not worsen from baseline is not considered an AE

## Serious Adverse Reaction (SAR)

Is an AE that fulfils the criteria for both a SAE and an AR

## Severity assessment definitions

Mild – No or transient symptoms, no interference with the patient’s daily activities.

Protocol  
Study ID: NN8640-4515  
UTN: U1111-1264-8642  
EU PAS No: Pending

~~CONFIDENTIAL~~

Date: 15 February 2022  
Version: 3.0  
Status: Final  
Page: 44 of 53

**Novo Nordisk**

Moderate – Marked symptoms, moderate interference with the patient’s daily activities.

Severe – Considerable interference with the patient’s daily activities, unacceptable.

### **Technical complaint**

A technical complaint is any written, electronic, or oral communication that alleges product (medicine or device) defects. The technical complaint may be associated with an adverse event but does not concern the adverse event itself.

Protocol  
Study ID: NN8640-4515  
UTN: U1111-1264-8642  
EU PAS No: Pending

~~CONFIDENTIAL~~

Date:	15 February 2022	Novo Nordisk
Version:	3.0	
Status:	Final	
Page:	45 of 53	

**Novo Nordisk**

## List of Stand-alone Documents

Number	Document reference number	Title
1	VV-TMF-4377145	Attachment I: Global List of key staff and relevant departments and suppliers of clinical relevance
2	Master Document: VV-TMF-4361535  Local signed documents will be filed for every participating country by the affiliate responsible person	Attachment II: Country list of key staff and relevant departments
3	Master Document VV-TMF-4436069	Agreement on protocol
4	Master document VV-TMF-4388758  Local translated documents will be filed for every participating country by the affiliate responsible person	Participation information and agreement to take part form

Protocol  
 Study ID: NN8640-4515  
 UTN: U1111-1264-8642  
 EU PAS No: Pending

**CONFIDENTIAL**

Date:  
 Version:  
 Status:  
 Page:

15 February 2022  
 3.0  
 Final  
 47 of 53

**Novo Nordisk**

## ANNEX 2. ENCePP Checklist for Study Protocols

### ENCePP Checklist for Study Protocols

**Study title:**

**A multi-national, multi-centre, prospective, single-arm, observational, non-interventional post-authorisation safety study to investigate long-term safety of Sogroya® (somapacitan) in adults with growth hormone deficiency (AGHD) under routine clinical practice**

**EU PAS Register® number: pending**

**Study reference number (if applicable): NN8640-4515**

Section 1: Milestones	Yes	No	N/A	Section Number
1.1 Does the protocol specify timelines for				
1.1.1 Start of data collection 				6
1.1.2 End of data collection 				6
1.1.3 Progress report(s)				
1.1.4 Interim report(s)				6
1.1.5 Registration in the EU PAS Register®				6
1.1.6 Final report of study results.				6

**Comments:**

Study will be registered in the EU PAS Register® prior to First patient first visit  
 Progress reports will be submitted in line with PSUR.

Section 2: Research question	Yes	No	N/A	Section Number
2.1 Does the formulation of the research question and objectives clearly explain:				
2.1.1 Why the study is conducted? (e.g. to address an important public health concern, a risk identified in the risk management plan, an emerging safety issue)				7
2.1.2 The objective(s) of the study?				8.1 -8.3

 Date from which information on the first study is first recorded in the study dataset or, in the case of secondary use of data, the date from which data extraction starts.

 Date from which the analytical dataset is completely available.

Protocol  
 Study ID: NN8640-4515  
 UTN: U1111-1264-8642  
 EU PAS No: Pending

**CONFIDENTIAL**

Date:  
 Version:  
 Status:  
 Page:

15 February 2022 | **Novo Nordisk**  
 3.0  
 Final  
 48 of 53

Section 2: Research question	Yes	No	N/A	Section Number
2.1.3 The target population? (i.e. population or subgroup to whom the study results are intended to be generalised)				9.2.4 9.7.2.2
2.1.4 Which hypothesis(-es) is (are) to be tested?				
2.1.5 If applicable, that there is no a priori hypothesis?				

Comments:

Section 3: Study design	Yes	No	N/A	Section Number
3.1 Is the study design described? (e.g. cohort, case-control, cross-sectional, other design)				9.1
3.2 Does the protocol specify whether the study is based on primary, secondary or combined data collection?				9.4
3.3 Does the protocol specify measures of occurrence? (e.g., rate, risk, prevalence)				9.1.1
3.4 Does the protocol specify measure(s) of association? (e.g. risk, odds ratio, excess risk, rate ratio, hazard ratio, risk/rate difference, number needed to harm (NNH))				
3.5 Does the protocol describe the approach for the collection and reporting of adverse events/adverse reactions? (e.g. adverse events that will not be collected in case of primary data collection)				11

Comments:

Not applicable for this study

Section 4: Source and study populations	Yes	No	N/A	Section Number
4.1 Is the source population described?				9.2
4.2 Is the planned study population defined in terms of:				
4.2.1 Study time period				6, 9.1
4.2.2 Age and sex				9.2.2
4.2.3 Country of origin				
4.2.4 Disease/indication				9.1
4.2.5 Duration of follow-up				9.1
4.3 Does the protocol define how the study population will be sampled from the source population? (e.g. event or inclusion/exclusion criteria)				9.2.2 9.2.3

Comments:

Country or origin isn't relevant for this study

Protocol  
 Study ID: NN8640-4515  
 UTN: U1111-1264-8642  
 EU PAS No: Pending

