**Figure 1 Study Design**

**Note:** symbol (  ) Represents interim reporting

The study is planned to collect a broad variety of safety and other clinical parameters data generated during routine clinical care visits and other relevant clinical contacts (e.g. phone calls between patient and clinical site) in AGHD patients treated with commercially available Sogroya® (somapacitan). The duration of the study is planned with patient participation for 5 years or longer up to a total study duration of 10 years, if possible. The main purpose of the study is to observe patients for long-term safety. It is however well known that adult patients on GH therapy, often interrupt or discontinue treatment. Due to this expected dropout from treatment, and in the context of the duration of the study, patients switching from or discontinuing treatment with Sogroya® (somapacitan) will be offered continuation in the study in order to collect post treatment data.

The current study will compare data from a non-interventional registry study (NordiNet® IOS) which was monitoring the long-term use of once daily Norditropin® as a historical comparison group consisting of approximately 2300 AGHD patients enrolled in Europe between 2006 and 2016.

The sample size estimation for this study is based on the incidences for neoplasms reported in Nordinet® IOS. It is estimated that a sample size of 400 patients will be required to rule out the doubling of incidence for neoplasms in patients treated with Sogroya® (somapacitan).

Data on concomitant medication, medical history (adult/ childhood onset of GHD), laboratory parameters including but not limited to hepatic, renal, heart and diabetes status as well as data on neoplasms and medication errors will be collected as part of this study if available per routine clinical practice in order to evaluate safety. Other data which are already available in the medical records or being obtained as part of routine clinical practice, such as IGF- I /IGFBP-3 values, measures of body composition and bone health and PROs, will be collected to support the evaluation of clinical parameters.

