### 9.5 Study sample size

#### Sample size calculations

The following table shows the 95% confidence interval for an incidence between 0% and 5%, like e.g. the incidence of neoplasm:

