**Table 1 Sample size calculations**

Sample size		Observed incidence					
		0%	0.5%	1%	2%	3%	4%
100	<3	-	0 – 5.4	0.2 – 7.0	0.6 – 8.5	1.1 – 9.9	1.6 – 11.3
200	<1.5	0 – 2.8	0.1 – 3.6	0.5 – 5.0	1.1 – 6.4	1.7 – 7.7	2.4 – 9.0
400	<0.75	0.1 – 1.8	0.3 – 2.5	0.9 – 3.9	1.6 – 5.2	2.3 – 6.4	3.1 – 7.6
600	<0.50	0.1 – 1.5	0.4 – 2.5	1.0 – 3.5	1.8 – 4.7	2.6 – 5.9	3.4 – 7.1

Using the observed incidence for neoplasm of 2% in the NordiNet® IOS with somatropin as reference values, a sample size of about 400 patients would be required to rule out the doubling of incidence for neoplasm. In general, the table shows that the precision, i.e. the change for the upper limit of the confidence interval, is having a large decrease when changing from 200 to 400 patients,

Protocol  
 Study ID: NN8640-4515  
 UTN: U1111-1264-8642  
 EU PAS No: Pending

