### 9.7.2 Statistical methods

#### 9.7.2.1 Analysis of primary endpoints

The primary endpoints are the number of Adverse Drug Reactions (ADRs), incident neoplasms, and incident T2D from baseline (week 0) up to end of study (week 520).

Frequencies of ADRs during the study period will be summarised by MedDRA SOC and PT. This summary is displayed with number and proportion of patients with at least one event, number of event and event rate (events per 100 patient-years of exposure).

The primary objective of the study is to evaluate safety of once weekly dosing of Sogroya® (somapacitan) in AGHD patients over a study period up to 10 years, and analysis of ADRs will be one of the tools for achieving this. Adverse drug reactions will be analysed using descriptive statistics based on the ‘on treatment’ observation period (primary evaluation) and ‘in-study’ observation period (secondary evaluation) within the study period. The ADRs will be summarised by treatment, MedDRA (Medical Dictionary for Regulatory Activities) system organ class and MedDRA preferred term. The descriptive statistics will include the number and percentage of patients who experienced ADRs, the number of events and rate per 100 person years. ADRs will be listed by treatment and patient with information on severity, relationship to study product and demographics. ADRs with onset before first dosing will be reported in a separate listing.

In addition, incidence rates will be calculated for the endpoints Neoplasm and Diabetes Mellitus type 2.

Results will be reported separately for treatment-naïve and prevalent users of GH replacement therapy, and patients with a history of neoplasia and diabetes mellitus 2 will be addressed in stratified analyses.

For historical reference the primary evaluation, i.e. the on-treatment analysis, will be compared to the same results reported from the Nordinet® IOS database. It is not expected that there will be big differences in the baseline characteristics between the Nordinet® adult population and the population investigated in this study. If there are big differences between baseline characteristics, a matching procedure will be considered when making the comparison. In addition, a sensitivity analysis will be performed, restricting the primary evaluation to a European population only.

Protocol  
 Study ID: NN8640-4515  
 UTN: U1111-1264-8642  
 EU PAS No: Pending

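### The study is sized to rule out a doubling of neoplasm incidence against NordiNet, but the primary analysis carries no criterion for doing so

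*Protocol*

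**What the plan says.** Section 9.1 gives the reason for the sample size: "It is estimated that a sample size of 400 patients will be required to rule out the doubling of incidence for neoplasms". Section 9.5 repeats it. It introduces Table 1 with "The following table shows the 95% confidence interval for an incidence between 0% and 5"%, takes its reference from the registry ("Using the observed incidence for neoplasm of 2% in the NordiNet" IOS), and concludes that "a sample size of about 400 patients would be required to rule out the doubling of incidence for neoplasm".

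Section 9.7.2.1 sets out the primary analysis. Adverse drug reactions are summarised descriptively. For the other two primary endpoints the text is: "In addition, incidence rates will be calculated for the endpoints Neoplasm and Diabetes Mellitus type 2". The on-treatment results are then to be set against those reported from NordiNet, with matching to be considered if baseline characteristics differ greatly. No ratio, difference, interval, margin or decision rule appears. Confidence intervals are mentioned only in Section 9.5.

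In the Annex 2 checklist, item 3.4 ("Does the protocol specify measure(s) of association? (e.g. risk, odds ratio, excess risk, rate ratio, hazard ratio" and so on) is ticked No, and the comment under that section says not applicable. Item 2.1.4 ("Which hypothesis(-es) is (are) to be tested") and item 2.1.5, on having no prior hypothesis, are both ticked N/A. Item 5.6 nevertheless states that an appropriate comparator is identified, citing Section 9.7.2.

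**The concern.** Ruling out a doubling is a statement about a ratio: the data must be incompatible with a value of 2 or more. The protocol uses that statement to fix the number of patients, then describes a primary analysis with nothing in it that decides whether the statement is met.

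The inferable criterion from Section 9.5 differs from the planned analysis in two ways. It concerns a proportion of patients, while Section 9.7.2.1 plans a rate. It also treats the NordiNet figure of 2% as known without error, although it is an estimate from about 2300 patients followed for a length of time that Section 9.5 does not give.

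The comparison with NordiNet is the only between-treatment conclusion in a safety study required by the regulator. If the measure is chosen once the data are known, that choice can decide whether the report says a doubling is excluded.

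**Working it through.** **Inputs.** From the protocol: N = 400 and a NordiNet neoplasm incidence of 2% (Section 9.5); a two-sided 95% interval (Section 9.5); about 2300 NordiNet patients (Section 9.1). Assumed, because the protocol does not give them: 46 NordiNet patients with a neoplasm (0.02 × 2300 = 46), binomial counts, and comparable follow-up in the two cohorts.

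**Step 1: reproduce the protocol's figure.** An observed 2% of 400 is 8 patients. The exact (Clopper-Pearson) limits are the 2.5% quantile of Beta(8, 393) and the 97.5% quantile of Beta(9, 392), which gives 0.87% to 3.90%. Table 1 prints 0.9 to 3.9, so the figure reproduces. Twice the reference is 2 × 2% = 4%, and 3.90% lies below it. With 9 patients the upper limit is the 97.5% quantile of Beta(10, 391), or 4.23%. The implied criterion is therefore met with at most 8 affected patients.

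**Step 2: the same data as a ratio.**
- Ratio = (8/400) / (46/2300) = 1.00.
- Standard error of the log ratio = √(1/8 − 1/400 + 1/46 − 1/2300) = √(0.1250 − 0.0025 + 0.0217 − 0.0004) = 0.379.
- 95% limits = exp(±1.96 × 0.379) = 0.48 to 2.10.

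The upper limit exceeds 2, so a doubling is not excluded. With 7 affected patients the ratio is 0.875 and its upper limit 1.92. On this measure at most 7 patients are allowed.

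**Step 3: how often each rule declares a doubling excluded.**

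| Rule | No true difference (2% and 2%) | True doubling (4% and 2%) |
|---|---|---|
| Single-arm upper limit below a fixed 4% | P(X ≤ 8; 400, 0.02) = 59% | P(X ≤ 8; 400, 0.04) = 2.0% |
| Single-arm upper limit below twice the NordiNet estimate | not needed here | about 3.3% |
| Upper limit of the ratio below 2 | about 44% | about 1.8% |

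The last two rows sum the joint binomial probabilities over both cohorts (400 and 2300 patients). The second row is the single-arm rule as it would work in practice, since the true NordiNet incidence is not known. The error rate then rises above the 2.5% that one tail of a 95% interval implies.

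**Step 4: follow-up.** At low incidence, the proportion affected is roughly the rate times the mean follow-up. Section 9.1.1 allows follow-up from 1 week to 10 years, and Section 9.5 attaches no follow-up to the NordiNet 2%. As an illustration only: if Sogroya patients were followed half as long on average, a doubled rate would appear as 2 × 0.5 × 2% = 2%. If they were followed twice as long, an equal rate would appear as 1 × 2 × 2% = 4%. A fixed 4% cannot separate these cases; a ratio of person-time rates can.

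**The case against.** The strongest reply is that Section 9.5 already supplies a route. A single-arm interval against twice the reference needs no measure of association, the planned counts are enough to compute it, and repeating the interval method in Section 9.7.2.1 is ordinary work for a statistical analysis plan, which is not at hand. This stands to a degree. A reader might infer that nothing planned could support the conclusion; that goes too far. What remains is that the inferable criterion is never stated as the analysis, uses a different quantity from the planned rate, and ignores the comparator's error and follow-up.

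Second, the checklist is weak evidence. Item 3.4 asks only whether a measure is specified, and No is a truthful answer. The same form ticks No for stratified and sensitivity analyses that Section 9.7.2 does plan. A reader might infer a considered decision that no contrast applies; a form completed this loosely does not show that. It supports the point only in that it agrees with Section 9.7.2.1. The N/A for hypotheses is also compatible with an estimation study, although ticking N/A for both 2.1.4 and 2.1.5 leaves the position unclear.

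Third, a reader might infer that two rates will simply be compared by eye, with any observed ratio below 2 taken as reassurance. The protocol states no such rule, so the point does not rest on it.

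Fourth, the doubling wording concerns neoplasm only. Nothing in the protocol sets such a criterion for type 2 diabetes or adverse drug reactions.

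Finally, the ratio rule weakens the argument for 400 patients. That is correct, and the fix states it as a cost.

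**Conclusion.** The point holds as an inconsistency between Sections 9.1 and 9.5 on one side and Section 9.7.2.1 on the other. The study is sized for a comparative conclusion that its primary analysis does not define. It goes beyond missing detail, because the one criterion that can be inferred gives the opposite answer to a ratio in the very scenario used to justify the sample size. Used against an estimated NordiNet rate, it also wrongly excludes a true doubling almost twice as often as the ratio rule does. All these figures assume binomial counts, 46 of 2300 NordiNet patients affected, and comparable follow-up. The sample size arithmetic itself is reproducible and is not in dispute. The change should be made before the first interim report, which is to use the same analysis as the final one.

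**What to change.** In Section 9.7.2.1:
- Define the NordiNet comparison of incident neoplasm as a person-time incidence rate ratio (Sogroya over NordiNet) with a two-sided 95% confidence interval that reflects the sampling error of both cohorts.
- State that a doubling is ruled out only if the upper limit is below 2.
- Report the same ratio and interval for incident type 2 diabetes, without a doubling criterion.

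In Annex 2, bring items 2.1.4, 2.1.5 and 3.4 into line with this text.

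In Section 9.5, say that with 400 patients, 2% in both cohorts and comparable follow-up, the chance of excluding a doubling is about 44% on the ratio, against 59% on the single-arm criterion.

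The cost is a few sentences, one simple model per endpoint and no new data collection in this study. It does need NordiNet person-time, and the protocol does not show that this is available. If it is not, the protocol should say so and withdraw the claim of ruling out a doubling. The report will also conclude more often that a doubling is not excluded.

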**CONFIDENTIAL**

Date:  
 Version:  
 Status:  
 Page:

15 February 2022 | **Novo Nordisk**  
 3.0  
 Final  
 49 of 53

Section 5: Exposure definition and measurement	Yes	No	N/A	Section Number
5.1 Does the protocol describe how the study exposure is defined and measured? (e.g. operational details for defining and categorising exposure, measurement of dose and duration of drug exposure)				
5.2 Does the protocol address the validity of the exposure measurement? (e.g. precision, accuracy, use of validation sub-study)				
5.3 Is exposure categorised according to time windows?				
5.4 Is intensity of exposure addressed? (e.g. dose, duration)				
5.5 Is exposure categorised based on biological mechanism of action and taking into account the pharmacokinetics and pharmacodynamics of the drug?				
5.6 Is (are) (an) appropriate comparator(s) identified?				9.7.2

Comments:

Treatment (dosing) according to normal practice and label. All relevant dosing and treatment information will be captured in the eCRF for this study

Section 6: Outcome definition and measurement	Yes	No	N/A	Section Number
6.1 Does the protocol specify the primary and secondary (if applicable) outcome(s) to be investigated?				9.1
6.2 Does the protocol describe how the outcomes are defined and measured?				9.1.1 9.2.7 9.2.8
6.3 Does the protocol address the validity of outcome measurement? (e.g. precision, accuracy, sensitivity, specificity, positive predictive value, use of validation sub-study)				
6.4 Does the protocol describe specific outcomes relevant for Health Technology Assessment? (e.g. HRQoL, QALYs, DALYS, health care services utilisation, burden of disease or treatment, compliance, disease management)				9.2.8.9

Comments:

Section 7: Bias	Yes	No	N/A	Section Number
7.1 Does the protocol address ways to measure confounding? (e.g. confounding by indication)				
7.2 Does the protocol address selection bias? (e.g. healthy user/adherer bias)				

Protocol  
 Study ID: NN8640-4515  
 UTN: U1111-1264-8642  
 EU PAS No: Pending

